### **Proposed statistical analysis for Aim 2: Functional Recovery and Symptoms**

We will analyze scores for each subscale of the KOOS-child, and the overall score produced by the pedi-IKDC range from 0 to 100, with higher scores indicating improved knee function. Each measure is approximately normal.

We describe the analysis for Aim 2, Sub-aim 2.1. The analyses for the other sub-aims are exactly parallel.

We plan to fit a general linear mixed model [39] with the pain subscale of the KOOS-child as the outcome. Predictors will include the visit at which the survey was given (6 weeks, 12 weeks, 6 months, 9 months and 12 months) and treatment group. Age will be included as a covariate. An unstructured covariance will be used to account for correlation between measurements on a single participant. If the resulting model fails to converge, a spatial exponential covariance will be used. Jackknifed-studentized residuals will be examined to assess normality, and transformations will be applied as appropriate.

We will test the null hypothesis of no polynomial time trend by treatment interaction. If the time-by-treatment test is non-significant, we will step down to test the main effects of time and treatment. Estimates, 95% confidence intervals, and p-values will be produced.

All hypothesis tests will be performed using the Wald test with Kenward and Roger degrees of freedom [40] . Three hypothesis tests may be performed for each outcome, for a total of 12 tests. To control for multiple comparisons, all hypotheses will be tested at the Bonferroni corrected alpha level of  $0.05/12=0.004$ .

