### **Power Analysis**

We conducted a power analysis for Aim 1, the primary endpoint of the study. The maximum sample size for the proposed trial is fixed at 12 patients per arm (24 participants total). The sample size is limited due to costs associated with dGEMRIC.

We calculated power for the test of no difference in T1GD between the treatment groups. We assumed a standard deviation of 50 ms for T1GD values, and a correlation of 0.2 between the baseline MRI and the 12-month T1GD measurements. Estimates were based on T1GD values reported by Neuman et al[42]. We expect T1GD values to be 85 ms higher in the injection group when compared to conservative therapy at the 6 month time point with no difference at baseline. We calculated power for 10, 11, or 12 participants per arm. Power was calculated using GLIMMPSE version 2.0.1.[43]

To detect a mean difference of 85 ms in T1GD between the treatment groups, power will be 0.93 with a Type I error rate of 0.05, for 12 participants per treatment group. To ensure a conclusive study, we will target an effective sample size of 10 participants per group. Over the 12 months, we expect to lose up to two participants per treatment group. To account for the attrition, we have set an enrollment goal of 24 participants, or 12 participants per treatment group.

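### The Aim 2 fallback covariance, a spatial exponential with no stated patient intercept, makes the step-down treatment test anti-conservative if children differ persistently; adding a random intercept is a cheap repair.

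*Combined protocol and SAP*

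**What the plan says.** The Aim 2 analysis section sets out one model for the KOOS-child pain subscale and applies it in the same way to the other three scores. On the mean: "Predictors will include the visit at which the survey was given (6 weeks, 12 weeks, 6 months, 9 months and 12 months) and treatment group". One adjustment term is named besides these: "Age will be included as a covariate". On the covariance: "An unstructured covariance will be used to account for correlation between measurements on a single participant", followed by the single contingency, "If the resulting model fails to converge, a spatial exponential covariance will be used". On testing, the interaction of treatment with a polynomial time trend comes first; then "If the time-by-treatment test is non-significant, we will step down to test the main effects of time and treatment". The test statistic is fixed for every step: "All hypothesis tests will be performed using the Wald test with Kenward and Roger degrees of freedom". On multiplicity: "Three hypothesis tests may be performed for each outcome, for a total of 12 tests", which sets the per-test alpha.

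No random intercept, nugget term, robust SE or check of fit is named for the fallback. The survey section has a baseline questionnaire completed, but the baseline score is not among the Aim 2 predictors. The Power Analysis section adds: "The maximum sample size for the proposed trial is fixed at 12 patients per arm (24 participants total".

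**The concern.** An exponential covariance ties all of a child's correlation to distance in time. If scores 6 weeks apart correlated 0.6, it would imply 0.6^(46/6) = 0.02 between week 6 and month 12. Self-reported knee scores may well carry a component that does not fade, such as underlying severity or reporting style. With the baseline score left out of the model, that component stays in the residuals.

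The treatment main effect compares averages over visits, and the variance of a child's average depends heavily on the long-range correlations. If the model sets these too low, it credits the trial with more information than it has. Kenward-Roger adjusts for estimating the covariance parameters in a small sample, not for a wrong covariance form. At stake are main-effect p-values that are too small and 95% intervals that are too narrow, on any of the four scores for which the fallback is used.

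**Working it through.** **Plan's own figure.** 3 tests x 4 outcomes = 12, and 0.05/12 = 0.00417, printed as 0.004. This reproduces. The plan gives no error rate for the fallback.

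**Inputs from the document.** Five post-baseline visits; visit, treatment and age in the model; 12 per arm (10 per arm after the expected attrition); Wald tests with Kenward-Roger degrees of freedom.

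**Assumptions.** Visits fall at weeks 6, 12, 26, 39 and 52. The true within-child covariance is not given, so several forms are tried.

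**Mechanism by hand.** Suppose the truth is compound symmetry with correlation r and unit variance. The variance of a child's five-visit mean is (1 + 4r)/5. The bare exponential that best fits that truth in likelihood gives:

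- r = 0.5: fitted variance 1.017, correlation 0.66 at 6 weeks and 0.04 at 46 weeks. Model variance of the mean is 0.417 against a true 0.600. SE ratio = sqrt(0.417/0.600) = 0.83.
- r = 0.7: fitted variance 1.011, correlation 0.81 and 0.20. Model variance 0.584 against a true 0.760. SE ratio = sqrt(0.584/0.760) = 0.88.

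Multiplying the t critical values on 22 df (2.074 at 0.05; 3.196 at 0.00417) by these ratios gives approximate error rates of 0.098 and 0.014 for r = 0.5, and 0.083 and 0.010 for r = 0.7. Estimating the covariance parameters from 24 children adds somewhat to this.

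**Simulation.** No treatment effect, complete data, 12 per arm, 30,000 trials per scenario, REML, first-order Kenward-Roger. The test is the treatment main effect; the last row used 6,000 trials per scenario.

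| Assumed truth and fitted model | Model SE / true SE | Error at 0.05 | Error at 0.0042 |
|---|---|---|---|
| Pure exponential, interaction kept | 1.01 | 0.048–0.049 | 0.003–0.004 |
| Compound symmetry 0.2–0.8, interaction dropped | 0.81–0.88 | 0.089–0.116 | 0.015–0.021 |
| Same, interaction kept | 0.83–0.91 | 0.079–0.108 | 0.011–0.020 |
| Intercept 30–70% of variance plus decay, interaction dropped | 0.86–0.92 | 0.072–0.095 | 0.009–0.015 |
| Same, interaction kept | 0.88–0.95 | 0.067–0.090 | 0.007–0.014 |
| Random intercept added to the fitted exponential (range over the truths tried) | 0.99–1.02 | 0.042–0.052 | 0.003–0.006 |

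A second simulation at 12 per arm gave 0.08 to 0.11 and 0.011 to 0.016 under compound symmetry, and 0.06 to 0.08 and 0.005 to 0.010 under intercept plus decay. With 10 per arm the picture is the same; the largest values were 0.115 and 0.023. An analysis of patient means adjusted for age held about 0.05 and 0.004 throughout, so the excess comes from the covariance form and not from the sample size.

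**The test that comes first.** The plan does not give the degree of the polynomial, so two versions were run in the persistent-difference scenarios at 12 per arm. The linear time-by-treatment test was conservative (0.00 to 0.02 at nominal 0.05). The 4-df test stayed near nominal at 0.05 (0.037 to 0.059) and ran from 0.0035 to 0.0078 at 0.0042.

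**The case against.** The strongest reply is that the fallback will seldom be used. Unstructured REML was fitted to 60 simulated trials in each of three settings: two dropouts per arm; 10 per arm with 10% intermittent missingness; and 12 per arm with both. It converged in all 180. This largely stands. It is a small check, with one optimiser and one assumed truth (compound symmetry 0.6): zero failures in 60 still allows a rate up to 1 - 0.05^(1/60) = 4.9% in any one setting, and heavier missingness could differ. Still, nothing in the documents suggests that non-convergence is likely.

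Second, the plan cites a random-effects paper for its mixed model, so an intercept may be intended. A citation does not put an intercept into the stated fallback, but its absence is read from silence and a clarification might settle the matter.

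Third, Aim 2 is not the primary endpoint, and the size rests on assumed covariances. Both are true.

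A reader might also infer more than the material supports:

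- That the fallback quadruples false positives in general. Fourfold or more is seen only at 0.0042 under assumed compound symmetry (0.021/0.00417 = 5.0 at the top). At 0.05 the largest multiple is 0.116/0.05 = 2.3.
- That every Aim 2 treatment test is affected alike. The clear inflation is in the step-down main effect; a linear interaction test loses power instead.
- That the model treats the five visits as almost independent. Under compound symmetry of 0.6 that would give an SE ratio of sqrt(0.20/0.68) = 0.54, far below the 0.81 to 0.91 found.

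**Conclusion.** The point holds as a conditional one. If the unstructured model fails to converge and children differ persistently, the stated fallback understates the SE of the treatment main effect by roughly 4 to 19%. Type I error is then about 0.08 to 0.12 at nominal 0.05 and 0.011 to 0.021 at 0.0042 under compound symmetry, or about 0.06 to 0.095 and 0.005 to 0.015 under intercept plus decay. If the correlation truly decays exponentially to zero, there is no inflation.

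If the fallback were used for all four scores, the Bonferroni bound for their main-effect tests would move from 4 x 0.00417 = 0.017 to between 4 x 0.011 = 0.044 and 4 x 0.021 = 0.084 under compound symmetry.

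The documents give neither correlations for these scores nor a basis for a failure rate, so they do not support a claim that the planned Aim 2 analysis is invalid or that its error rate will be inflated. This is a cheap improvement of low priority.

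**What to change.** In the Aim 2 section, restate the fallback as a random patient intercept plus a spatial exponential residual, with actual weeks as the distance, and keep the Wald tests with Kenward-Roger degrees of freedom. Across the truths tried, this brings the main-effect error to about 0.04 to 0.05 at nominal 0.05 and 0.003 to 0.007 at 0.0042. If an intercept was always intended, the same sentence makes it explicit.

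The cost is one sentence of text, one line of model code and one more variance parameter to estimate from at most 24 children, and only in the event that the unstructured model fails. The change should be made before outcome data by arm are seen, so that the fallback is not chosen after the fact.

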**2. Specific Aims:**

In adolescents with osteochondritis dissecans of the knee:

**Aim 1.** Compared to conservative therapy alone, determine whether intra-articular platelet injections combined with conservative therapy lead to greater cartilage healing.

**Efficacy Endpoint** – Measurement by glycosaminoglycan (GAG) content (T1GD) on dGEMRIC, or by healing changes of MRI diagnostic cartilage sequences, using the DiPaola classification system.

**Aim 2.** Compared to conservative therapy, determine whether intra-articular platelet injections lead to improvements over time in:

**Efficacy Endpoint 2.1.** Pain, as measured by the pain subscale of the KOOS-child.

**Efficacy Endpoint 2.2.** Performance of activities of daily living, as measured by the ADL subscale of KOOS-child.

**Efficacy Endpoint 2.3.** Sport performance, as measured by the sports subscale of the KOOS-child.

**Efficacy Endpoint 2.4.** Overall function and symptom reduction, as measured by the pedi-IKDC.

**Aim 3.** Correlate dGEMRIC findings or MRI diagnostic cartilage sequence findings on imaging studies with measures of functional recovery and symptom reduction.

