### **Proposed statistical analysis for Aim 1: Cartilage healing**

The T1GD value on dGEMRIC measures GAG content in cartilage. Higher T1GD values are associated with higher GAG content in the tissue, a positive measure of cartilage health. We assume that the value is approximately normal.

We plan to fit a general linear mixed model [39] for the outcome of T1GD. Predictors will include the visit at which the T1GD test was performed (initial MRI and 6 months), whether the site was weight bearing or not, and whether the side was affected or not, and the treatment group. Age will be included as a covariate. An unstructured covariance will be used to account for correlation between T1GD measurements on the same participant. Jackknifed-studentized residuals will be examined to assess normality, and transformations will be applied as appropriate.

We will test the null hypothesis of no time by treatment by weight bearing surface by affected side interaction. Given a non-significant interaction, we will test the main effects of time and treatment, comparing the difference between the weight-bearing and non-weight bearing surface for the affected and non-affected sides. Estimates, 95% confidence intervals, and p-values will be produced. All hypothesis tests will be performed using the Wald test with Kenward and Roger degrees of freedom[40] . Hypothesis tests will be performed at the Bonferroni corrected alpha of  $0.05/3 = 0.017$ .

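### The Aim 2 correction is valid but stricter than it needs to be: a third of the alpha goes to time main effects that do not compare the arms, and Holm over the eight treatment tests recovers modest power

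*Combined protocol and SAP*

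**What the plan says.** Section 2 (Specific Aims) frames Aim 2 as a comparison with conservative therapy: to "determine whether intra-articular platelet injections lead to improvements over time in" four scores, namely the pain, ADL and sports subscales of the KOOS-child and a fourth endpoint, "Overall function and symptom reduction, as measured by the pedi-IKDC".

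The proposed statistical analysis for Aim 2 sets out the same tests for each score. The first is the interaction: "We will test the null hypothesis of no polynomial time trend by treatment interaction". Two more may follow: "If the time-by-treatment test is non-significant, we will step down to test the main effects of time and treatment". The count and the level are then fixed: "Three hypothesis tests may be performed for each outcome, for a total of 12 tests", and "To control for multiple comparisons, all hypotheses will be tested at the Bonferroni corrected alpha level of" 0.05/12 = 0.004. The 95% confidence intervals in the same section are not adjusted for multiplicity.

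The Power Analysis section calls Aim 1 the primary endpoint and covers that aim only. It caps enrolment at 12 per arm and targets an effective 10 per arm after attrition.

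**The concern.** The 12 tests are of three kinds, four of each. The interactions and the treatment main effects compare the arms. The time main effects do not: they ask whether the average score changes over follow-up with the arms taken together. The part of Aim 2 that concerns change over time is already tested by the interaction. The Preliminary Studies section expects most of these patients to heal within a year without treatment, so a significant time effect would be unsurprising and would say nothing about PRP. No sub-aim asks for it. Each time test nevertheless lowers the threshold for the tests that do address Aim 2.

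In addition, plain Bonferroni holds every test at the same level however many hypotheses have been rejected. Holm's procedure gives the same family-wise guarantee under any dependence and rejects everything that Bonferroni rejects on the same family. With 10 to 12 patients per arm, and the number capped by imaging cost, power that can be had from the analysis alone is worth taking.

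**Working it through.** **The plan's figure.** 3 tests x 4 outcomes = 12, and 0.05/12 = 0.00417, printed as 0.004. The rounding is on the safe side: 12 x 0.004 = 0.048.

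**Where the alpha goes.**
- Time main effects: 4 x 0.05/12 = 0.0167, one third of 0.05.
- Tests that compare the arms: 8 x 0.05/12 = 0.0333.
- If the eight share the full 0.05, each gets 0.05/8 = 0.00625, which is 1.5 times 0.00417. Holm over the eight uses 0.05/8, 0.05/7, ..., 0.05 on the ordered p-values.

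**Assumptions for power.** The documents give no effect size, SD or correlation for Aim 2 and do not state sidedness. I assume two-sided tests, a two-sample t approximation, the same true treatment main effect on all four scores, no true interaction, and a correlation of 0.6 between scores. Effects range from 0.8 to 1.6 SD, with 12 and 10 per arm taken from the Power Analysis section.

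**One test.** Power is P(|T| > t(1 - alpha/2; 2n - 2)), with T noncentral t on 2n - 2 degrees of freedom and noncentrality d x sqrt(n/2). For d = 1.3 and n = 12 the noncentrality is 1.3 x sqrt(6) = 3.18. Power is 0.50 at 0.004 and 0.57 at 0.05/8. The difference detectable with 80% power falls from 1.68 to 1.60 SD with 12 per arm, and from 1.88 to 1.79 SD with 10 per arm.

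**Four outcomes, 20,000 simulated trials per setting, average power per outcome.**

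| Per arm | True effect | Plan (0.004) | Holm over 8 |
|---|---|---|---|
| 12 | 0.8 SD | 0.14 | 0.19 |
| 12 | 1.3 SD | 0.50 | 0.60 |
| 12 | 1.6 SD | 0.75 | 0.83 |
| 10 | 0.8 SD | 0.10 | 0.14 |
| 10 | 1.3 SD | 0.38 | 0.48 |
| 10 | 1.6 SD | 0.61 | 0.71 |

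At 1.3 SD and 12 per arm, removing the time tests gives 0.50 to 0.57 and Holm adds the rest, 0.57 to 0.60. The chance of at least one significant outcome rises from 0.785 to about 0.84. All of that comes from removing the time tests, because Holm's first step is the same as Bonferroni's. With all eight null hypotheses true, simulated family-wise error under Holm is 0.043.

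**A second model.** A simulation closer to the planned analysis used five visits, a linear trend contrast, correlation 0.5 between visits and 0.6 between outcomes, and a 1.0 SD effect at every visit. With 12 per arm it gave 0.50 as planned, 0.57 with Bonferroni over 8 and 0.60 with Holm over 8. With 10 per arm it gave 0.38, 0.44 and 0.47 to 0.48. It evaluated all tests and did not apply the rule that main effects follow only a non-significant interaction.

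**The case against.** The strongest reply is that nothing here is wrong. The plan prespecifies a conservative correction and applies it to every hypothesis it declares. A time effect that carries a p-value may reasonably be counted. Aim 1 is primary, no power is promised for Aim 2, and so no stated figure fails. All of this stands, and it limits the point to efficiency.

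It also stands that the sample size is the main constraint. At 0.8 SD and 12 per arm, the chance of any significant outcome moves only from 0.32 to just under 0.40. A reader might infer that the correction decides whether a clinical benefit can be shown at all. The documents give no Aim 2 effect size or SD to support that, and Holm does nothing for the first rejection.

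One could keep all 12 tests and apply Holm to them. In the five-visit simulation (1.0 SD, 12 per arm) this matches Holm over 8 when all the time effects are significant, because their alpha passes on. With no time trend it gives 0.52 against 0.60. Removing the time tests is therefore the surer gain.

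A reader might go further and correct for only four tests, one per outcome. That means choosing the interaction or the treatment main effect as the sole confirmatory test. The plan names neither, and its aims speak of both improvement over time and a difference between arms. The choice would change the question, so it is not a free gain.

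A reader might also see an overspend in Aim 1, where 3 x 0.017 = 0.051. The plan prints the exact fraction 0.05/3 beside it, so 0.017 is only a rounded display.

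**Conclusion.** The point holds as a free but modest efficiency gain in a secondary aim. One third of the Aim 2 alpha goes to tests that do not compare PRP with conservative therapy, and single-step Bonferroni gives up a little more. Over the assumed range of effects, average power per outcome rises by 0.05 to 0.10 with 12 per arm and by 0.04 to 0.10 with 10 per arm.

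The alpha arithmetic follows from the plan alone. The power figures depend on the assumed effects, the correlation of 0.6, a true effect confined to the treatment main effect, and a two-sample t approximation to the planned mixed model. A reader might take the point to mean that the plan fails to control its error rate. It does not: the planned correction is valid and conservative.

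**What to change.** In the Aim 2 analysis section:

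1. Take the four time main effects out of the corrected family and report them descriptively, with estimates and intervals.
2. Define the family as eight tests: four time-trend-by-treatment interactions and four treatment main effects.
3. Replace the fixed 0.004 with Holm at an overall 0.05, run on all eight p-values.
4. State how this fits the existing order of testing: a treatment main effect is claimed only if Holm rejects it and does not reject that outcome's interaction. The claims are then a subset of Holm's rejections, so family-wise error stays at or below 0.05.

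The cost is SAP wording, to be settled before the treatment codes are revealed. No patients, visits or data are added. What is given up is a formal test of the time effect, which no sub-aim requests. Holm has no simple matching simultaneous intervals, but the planned 95% intervals are already unadjusted, so no planned output is lost.

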### **Proposed statistical analysis for Aim 3: Correlation of MR Findings and Measures of Functional Recovery and Symptoms**

We plan to fit four general linear univariate models with 6-month T1GD as the outcome. The primary predictor for each model will be the 6 month measurements of the pain subscale of KOOS-child, the ADL subscale of the KOOS-child, the sports subscale of the KOOS-child, and the pedi-IKDC, respectively. In each model, age will be included as a covariate. We will test the null hypothesis of no association between the functional measure and T1GD findings on MR and/or no decrease in DiPaolo score, using an F test. All hypotheses will be tested at the Bonferroni corrected alpha level of  $0.05/4 = 0.0125$ .

Interim analysis and planned interim power analysis.

Because this study has never been done in children, the estimates for power analysis may be incorrect, and the effect of the treatment may be better or worse than that reported in the literature. Thus, after the first six study participants have been recruited, treated, and followed, the investigators will report blinded data to the study statistician, who will perform an interim power analysis using the methods of Gurka et al., 2007 [41].

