## **Informational patient brochure/Compliance Surveys/ Baseline and Follow-up KOOS and IKDC surveys/Clinical Assessments**

An informational brochure (see attached) will be used to assist in the recruitment of eligible patients. The brochure will describe the autologous platelet rich plasma treatment, process, risks, appointment information and post procedure information.

Patients randomized to the PRP Treatment arm will receive a Pre and Post-Injection Instruction handout (see attached). The handout describes how the patient should prepare for the PRP injections and what to expect after the injection.

The study personnel who consents the patient will request the patient's and parent's email addresses which will be used to send out the weekly and monthly surveys.

For the first 6 weeks of the study, all patients will receive a weekly Compliance Survey (see attached) created by the Sports Medicine physicians to validate compliance with 1. non-weight bearing, 2. wearing a brace, 3. at home PT exercises, and 4. no high impact activity.

**KOOS/IKDC surveys:** All patients will receive a baseline survey and repeat surveys at 6 wks, 12 wks, 6 m, 9m, and 12 months, which is considered standard of care, on the CHCO main campus or one of the following satellite locations (South, Parker, Centennial, Uptown/St Joseph's or Broomfield). The surveys will include the following outcome scales: Pedi IKDC and KOOS-child.

The Pedi-IKDC is a modified version of the widely used International Knee Documentation Committee (IKDC) Subjective Knee Form, which is a knee specific measure of symptoms, function and sports activity. The Pedi-IKDC was developed for use with children and adolescents ages 10-17. The reliability and validity of the Pedi-IKDC has been demonstrated to be acceptable in young patients with a variety of knee disorders.

Similarly, the KOOS – child is a pediatric version of the Knee Injury and Osteoarthritis Outcome Score (KOOS). The KOOS-child score is subdivided and scored in five categories: Pain, Other Disease-Specific Symptoms, Activities of Daily Living Function (ADL), Sport and Recreation Function and Knee-related Quality of Life (QOL).

[http://www.actaorthop.org/sup\\_files/5292.pdf](http://www.actaorthop.org/sup_files/5292.pdf)

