Each patient will have four values of GAG (T1GD) measured at the baseline MRI and again at the 6 month MRI, via dGEMRIC. The locations of the measurements will be designated using the lateral view of the femoral condyle as a clock face with the medial femoral condyle superior location being designated as 12 o'clock, the inferior location being designated as 6 o'clock and the anterior location being designated as 3 o'clock; the lateral view of the femoral condyle as a clock face with the lateral femoral condyle superior location being designated as 12 o'clock, the inferior location being designated as 6 o'clock and the anterior location being designated as 9 o'clock. The values will be measured at four locations: the medial side at a weight bearing surface, the medial side at a non-weight bearing surface of the posterior condyle (4 o'clock), the lateral side at a weight bearing surface, and the lateral side at a non-weight bearing surface of the posterior condyle (8 o'clock). The side with the lesion will be designated as the affected side, and the side without the lesion will be designated as the non-affected side. GAG (T1GD) will be measured on the affected weight bearing surface at the site of the lesion. GAG (T1GD) will be measured on the non-affected side at the corresponding weight bearing surface of the femoral condyle.

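### Aim 3 speaks of functional recovery and symptom reduction, but its four models use 6-month values and age only and leave out the baseline T1GD and baseline scores that the trial collects

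*Combined protocol and SAP*

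**What the plan says.** Section 2 (Specific Aims) gives Aim 3 as: "Correlate dGEMRIC findings or MRI diagnostic cartilage sequence findings on imaging studies with measures of functional recovery and symptom reduction". Section 4 (Research Methods) repeats that goal.

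The Aim 3 analysis section puts it into practice as follows.
- Outcome: "We plan to fit four general linear univariate models with 6-month T1GD as the outcome".
- Predictor: "The primary predictor for each model will be the 6 month measurements of the pain subscale of KOOS-child" in the first model, and the 6-month KOOS-child ADL, KOOS-child sports and pedi-IKDC scores in the other three.
- Covariates: "In each model, age will be included as a covariate". No other covariate is named.
- Null hypothesis: "no association between the functional measure and T1GD findings on MR and/or no decrease in DiPaolo score, using an F test". The DiPaola decrease is the only element of change, and none of the four models carries it, since all have T1GD as outcome.

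The baseline data exist. On imaging: "Each patient will have four values of GAG (T1GD) measured at the baseline MRI and again at the 6 month MRI". On the scores: "All patients will receive a baseline survey and repeat surveys at 6 wks, 12 wks, 6 m, 9m, and 12 months". The rules under 6 month Research MRIs give a 6-month dGEMRIC only to patients whose initial scan was a dGEMRIC, so every 6-month T1GD value should have a baseline partner. The Aim 1 model uses both scans; the Aim 3 models use only the later one.

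**The concern.** In their ordinary sense, recovery and symptom reduction describe movement from a starting point. A 6-month level mixes that movement with where the patient began. The inclusion criteria admit DiPaola grades 1 and 2, so starting severity can differ. A patient who enters with a mild lesion and a good score may well show high T1GD and a high score at 6 months without having changed. A patient who gains a great deal from a low start may still rank low on both.

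A significant Aim 3 result could therefore reflect persistent severity rather than imaging that follows recovery, and the planned models offer no way to tell the two apart.

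The outcome is also not fully defined. Each model needs one T1GD value per patient, but the dGEMRIC section gives four locations per scan, only one of them at the lesion. The Data Analysis Plan describes a different set: lesion, adjacent and distant. The Aim 3 section does not say which value is analysed. This is a separate gap from the missing baselines, but the same sentence can close it.

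**Working it through.** **The plan's own figure.** The Aim 3 alpha is 0.05/4 = 0.0125, which reproduces. The plan gives no power or sample size for Aim 3.

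**Inputs from the documents (Power Analysis)**
- T1GD correlation between scans: 0.2. It is stated for baseline to 12 months; I use it for baseline to 6 months because no 6-month value is given.
- Patients: 10 per arm after dropout, so n = 20. This is the most favourable reading, because only dGEMRIC patients have T1GD.

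**Assumptions (not in the documents)**
- Correlation of the functional score between baseline and 6 months, rF: 0.4 to 0.7.
- Correlation between the stable components of T1GD and score, rb: 0, 0.5 and 0.9.
- No treatment effect, and equal variances at the two visits.

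**Set-up.** Each standardised measure is a stable patient component plus independent visit noise. For T1GD with rT = 0.2, value = √rT × stable part + √(1 − rT) × noise, and likewise for the score with rF. The visit noise is independent between T1GD and score, so the changes are unrelated by construction. The implied correlation between the two 6-month levels is rb × √(rT × rF). For example, 0.5 × √(0.2 × 0.4) = 0.141 and 0.9 × √(0.2 × 0.7) = 0.337.

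**Rejection rates at alpha 0.0125, n = 20, 20,000 simulated trials per row**

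| rF | rb | Implied 6-month correlation | Planned model | Plus both baselines | Change on change |
|---|---|---|---|---|---|
| 0.4 | 0 | 0 | 1.2% | 1.1% | 1.3% |
| 0.4 | 0.5 | 0.141 | 2.8% | 1.6% | 1.2% |
| 0.4 | 0.9 | 0.255 | 6.8% | 2.6% | 1.2% |
| 0.7 | 0 | 0 | 1.2% | 1.3% | 1.3% |
| 0.7 | 0.5 | 0.187 | 3.9% | 1.6% | 1.2% |
| 0.7 | 0.9 | 0.337 | 13.0% | 2.4% | 1.3% |

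A separate run with a different random seed agreed to within simulation error. The planned model's excess appears only when rb is above zero. Adding both baselines removes most of it, but not all.

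The result depends on the borrowed 0.2. With an assumed T1GD correlation of 0.5, and rb of 0.5 to 0.9, the planned model's range at n = 20 is 5.5% to 45.4%. The documents do not support that value, so I do not rely on it.

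**Cost of the two extra covariates.** The critical partial correlation is t/√(t² + df), with t the two-sided critical value at 0.0125.
- n = 20, planned model: df = 17, t = 2.793, giving 0.56. With both baselines: df = 15, t = 2.837, giving 0.59.
- n = 10 (assumed, if few patients have dGEMRIC): df falls from 7 to 5 and the threshold rises from 0.78 to 0.86.

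**The case against.** **Aim 3 may be meant as cross-sectional.** Endpoint 2.4 already uses symptom reduction as a label for what the pedi-IKDC measures, so "with measures of functional recovery and symptom reduction" may simply name the instruments. On that reading a 6-month association is what was asked for. This stands as a possible reading. A reader might infer that the planned models leave Aim 3 wholly unanswered, and the documents do not support going that far. What remains is that the plan does not say which reading it intends.

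**Change is not wholly absent.** The null hypothesis mentions a DiPaola decrease, and the dGEMRIC section uses that grade for interval change on non-contrast scans. This is true, but no specified model tests it.

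**Age is already in the models.** This also stands. The 10 to 17 age range is therefore no argument for unadjusted differences in starting level; starting severity is.

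**Baseline T1GD may matter little.** At a correlation of 0.2 it explains only 0.2² = 4% of the 6-month variance. The distortion then depends largely on score correlations that the documents do not give, and it vanishes if the stable components are uncorrelated.

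**A tempting but unsupported measure of size.** With equal variances, the correlation of the 6-month level with change is √((1 − r)/2). At r = 0.2 this is 0.63, and a reader might infer that the level captures only 40% of the variance in healing. Corresponding shares for the scores, at assumed correlations of 0.5 and 0.7, would be 25% and 15%. These figures do not measure confounding by starting level, because even r = 0 gives only 50%. The T1GD figure also borrows a 12-month correlation and ignores the 85 ms arm difference expected at 6 months. With the arms pooled, 6-month variance is 2500 + 42.5² = 4306, the covariance with baseline is 0.2 × 2500 = 500, and the variance of change is 4306 + 2500 − 1000 = 5806. The correlation is then (4306 − 500)/√(4306 × 5806) = 0.76, or 58%. None of these shares should be used.

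**Conclusion.** The concern holds in a limited form. The four Aim 3 models contain no baseline information although paired values are collected, so they cannot separate recovery from persistent severity. Under the assumed correlations and with n = 20, the planned test rejects in about 3% to 13% of trials when changes are unrelated, against a nominal 1.25%. With both baselines added the figure is about 1.5% to 2.6%. These rates illustrate a possible distortion; they do not show that it will occur, and with uncorrelated stable components there is none.

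A reader might also infer that baseline adjustment turns the score coefficient into change related to change. It does not: the coefficient is a partial association given both starting levels, which is why a small excess remains.

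The Power Analysis names Aim 1 as the primary endpoint, and nothing here affects Aim 1. This is a worthwhile, low-cost improvement to a non-primary aim.

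**What to change.** In the Aim 3 analysis section:
- Name the outcome as 6-month T1GD at the affected weight-bearing surface, that is, the lesion site.
- Add two covariates beside the 6-month score and age: baseline T1GD at the same site, and the baseline value of the same functional score.
- Describe the score coefficient as an association adjusted for starting level.
- Add a model of T1GD change on score change, with age, as a sensitivity analysis.
- Report the unadjusted 6-month association as descriptive and cross-sectional only.

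The cost is SAP wording and two residual degrees of freedom per model. At n = 20 that is a modest loss. If few patients have dGEMRIC, the loss is larger, and the number with paired T1GD should be reported beside each result. No new data collection is needed.
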